9.8.2 Rash

Individuals who develop a generalized rash will be monitored closely. Study drug dosing should be interrupted if a subject develops a generalized rash of Grade 3 or higher, or a rash that is considered a serious adverse event. The investigator will notify the medical monitor of any rash that results in interruption of study drug, is Grade 3 or higher (Section 13.1.1.4), or is a serious adverse event (SAE). Investigators should consider additional evaluation including laboratory testing (e.g., complete blood count [CBC] with differential, LFTs), photographs of the rash, and dermatology consultation. The investigator may consider resumption of study drug if considered clinically appropriate.

9.9 Removal of Subjects

Subjects may withdraw from the study at any time at their own request. Subjects may be withdrawn from study drug treatment at any time at the discretion of the investigator or Vertex for safety, behavior, noncompliance with study procedures, or administrative reasons. If a subject has been withdrawn from study drug treatment, the subject will continue to be followed, provided that the subject has not withdrawn consent (and assent, as applicable).

In addition, a subject must be discontinued from study drug treatment if the subject meets any of the following criteria:

- Meets any of the stopping (discontinuation) criteria (Section 9.7)
- Becomes pregnant (Section 11.7.7.2)

If a subject does not return for a scheduled visit, reasonable effort will be made to contact the subject. In any circumstance, reasonable effort will be made to document subject outcome. The investigator will inquire about the reason for withdrawal, request that the subject return all unused investigational product(s), request that the subject return for an ETT Visit and Safety Follow-up Visit, if applicable (see Section 9.1.3), and follow up with the subject regarding any unresolved AEs.

If the subject withdraws consent or assent for the study, no further assessments will be performed. Vertex may retain and continue using the study data and samples after the study is over, and may use the samples and information in the development of the study compound, and for other drugs and diagnostics, in publications and presentations, and for education purposes. If the subject withdraws from the study, the study data and samples collected will remain part of the study. A subject will not be able to request the withdrawal of his/her information from the study data. A subject may request destruction of the samples collected from him/her during the study as long as those samples can be identified as his/her samples.

If evaluation of efficacy data from the parent studies suggests that the VX-659/TEZ/IVA treatment does not provide clinically meaningful benefit for subsets of subjects included in these studies, Vertex may recommend that subjects with relevant genotypes discontinue from the study. In addition, if local health authorities decline to approve VX-659/TEZ/IVA, or if clinical benefit is not demonstrated for the use of VX-659/TEZ/IVA for the treatment of CF in specific subpopulations enrolled in this study, subjects with the relevant *CFTR* genotypes may be

discontinued after communication to investigators and IRBs/IECs of the risks/benefits related to the safety and efficacy observed for the relevant subset of subjects.

9.10 Replacement of Subjects

Subjects who withdraw or are withdrawn during the study drug treatment period will not be replaced.

10 STUDY DRUG INFORMATION AND MANAGEMENT

Study drug refers to VX-659/TEZ/IVA and IVA.

10.1 Preparation and Dispensing

Study drug may be dispensed only under the supervision of the investigator or an authorized designee and only for administration to the study subjects.

10.2 Packaging and Labeling

Study drug tablets will be supplied in blister cards by Vertex. Study drug labeling will be in compliance with applicable local and national regulations. Additional details regarding packaging, labeling, and dispensing for study drug will be in the Pharmacy Manual.

10.3 Study Drug Supply, Storage, and Handling

VX-659/TEZ/IVA will be supplied as 2 FDC film-coated tablets containing 120 mg VX-659/50 mg TEZ/75 mg IVA (Table 10-1).

IVA (150 mg) will be supplied as tablets containing 150-mg IVA (Table 10-1).

Blister cards must be stored under conditions noted in the Pharmacy Manual. The investigator, or an authorized designee (e.g., a licensed pharmacist), will ensure that all investigational product is stored in a secured area, under recommended storage conditions, and in accordance with applicable regulatory requirements. To ensure adequate records, all study drugs will be accounted for via the drug accountability forms as instructed by Vertex.

Table 10-1 Study Drug: Strength/Dosing Form/Route

Drug Name, Dosing Form, Route	Strength
VX-659/TEZ/IVA, FDC tablet, oral	
VX-659	120 mg
TEZ	50 mg
IVA	75 mg
IVA, tablet, oral	150 mg

FDC; fixed-dose combination; IVA: ivacaftor; TEZ: tezacaftor

10.4 Drug Accountability

The pharmacist or designated study site staff will maintain information regarding the dates and amounts of (1) study drug received; (2) study drug dispensed to the subjects; and (3) study drug returned by the subjects. Subjects will be instructed to return all used and unused materials associated with the study drug to the site. These materials will be retained at the site according to instructions provided by Vertex or its designee. The study monitor will review study drug records and inventory throughout the study.

If a site uses a site-specific drug accountability system and/or process, including processes associated with the destruction of returned materials, the process must be documented and approved by Vertex. The study monitor must review the drug accountability documentation on a regular basis. The study monitor will promptly communicate to Vertex any discrepancies he/she is unable to resolve with the site.

10.5 Disposal, Return, or Retention of Unused Drug

The study site staff or pharmacy personnel will retain all materials returned by the subjects until the study monitor has performed drug accountability. The investigator will ensure that the materials are destroyed in compliance with applicable environmental regulations, institutional policy, and any special instructions provided by Vertex. Destruction will be adequately documented.

10.6 Compliance

To ensure treatment compliance, the investigator or designee will supervise all study drug dosing that occurs at the site. At each visit, site personnel will review that the subject is compliant with study drug dosing and remind the subject of study drug dosing requirements. Compliance will also be assessed by ongoing study drug count.

If a subject demonstrates continued noncompliance of study drug dosing despite educational efforts, the investigator should consider discontinuing the subject from the study.

10.7 Blinding and Unblinding

This will be an open-label study. However, as outlined in Section 11.4 and Section 11.6.1, subjects (and their parents/caregivers/companions) should not be informed of their study-related spirometry and SwCl results until Vertex has determined that the study has completed (i.e., CSR finalization). Individual SwCl test results will also not be disclosed to the study sites. In addition, the Vertex study team will not have access to the spirometry or SwCl results of the present study until the database lock of the parent study.

11 ASSESSMENTS

11.1 Timing of Assessments

The timing of assessments is shown in Section 3 and Table 3-1.

11.2 Subject and Disease Characteristics

Subject and disease characteristics include the following: demographics, medical history, height, and weight. Select demographic and baseline characteristic data and medical history will be derived from the parent study.

11.3 Pharmacokinetics

11.3.1 Blood Sampling

At the Week 4 Visit only, predose blood samples will be collected to determine plasma concentrations of VX-659, TEZ, M1-TEZ, and IVA. These samples may also be used to evaluate metabolites of VX-659 and additional TEZ and IVA metabolites. [REDACTED]

The Week 4 predose samples must be collected within 60 minutes before dosing; all efforts should be made to obtain the PK samples during this specified window. Samples collected outside of the window will be considered protocol deviations.

A record of study drug administration that coincides with the Week 4 PK blood draw will be collected as described in Section 9.6. The collection date and exact time that each PK blood sample is drawn will also be recorded.

Samples from the PK sampling will be kept frozen by Vertex or its designee until all analyses have been completed and then disposed of according to Vertex or designee standard operating procedures.

11.3.2 Processing and Handling of Pharmacokinetic Samples

Detailed procedures for the collection of blood samples and further procedures for processing and handling of samples for PK analysis will be provided in the PK Sample Handling Guidelines.

11.3.3 Bioanalysis

Samples will be analyzed using validated analytical methods in compliance with Vertex or designee standard operating procedures. A description of the assays and validation data will be provided in separate reports.

11.4 Pharmacodynamics: Sweat Chloride

SwCl samples will be collected with an approved collection device. Each collection will occur before study drug dosing (Section 9.6.1). At each time point, 2 samples will be collected; 1 from each arm (left and right). Sweat samples will be sent to a central laboratory for testing and interpretation of results. Individual SwCl test results will not be disclosed to the study sites. Specific instructions for the collection, handling, processing, and shipping of SwCl samples to the central laboratory will be provided separately.

Subjects (and their parents/caregivers/companions) should not be informed of their study-related SwCl results until Vertex has determined that the study has completed (i.e., CSR finalization), regardless of whether the subject has prematurely discontinued treatment.

11.6 Efficacy

11.6.1 Spirometry

Spirometry will be performed according to the American Thoracic Society Guidelines/European Respiratory Society Guidelines⁹ and according to the additional guidelines that follow.

Pre-bronchodilator spirometry is defined as spirometry testing performed for subjects who have

- withheld their short-acting bronchodilators (e.g., albuterol) or anticholinergic (e.g., ipratropium bromide [Atrovent[®]]) for more than 4 hours before the spirometry assessment;
- withheld their long-acting bronchodilator (e.g., salmeterol) for more than 12 hours before the spirometry assessment; and
- withheld their once-daily, long-acting bronchodilator (e.g., tiotropium bromide [Spiriva[®]]) for more than 24 hours before the spirometry assessment.

All spirometry assessments should be performed pre-bronchodilator. During the Treatment Period, spirometry assessments must be performed before study drug dosing (Section 9.6.1) at approximately the same time at each visit. In the event that a subject forgets to withhold bronchodilator(s), spirometry should be performed according to the following:

- If a subject's Day 1 spirometry assessment from the parent study is pre-bronchodilator, but on a subsequent visit in this study, the subject forgets to withhold bronchodilator use, a post-bronchodilator spirometry assessment will be obtained for that visit only and the visit will not be rescheduled.
- If, on Day 1 of the parent study, the subject forgot to withhold his/her dose of bronchodilator, spirometry should be performed post-bronchodilator and all subsequent spirometric

measurements in this study (according to the schedule of assessments detailed in [Table 3-1](#)) should be performed post-bronchodilator.

- Each spirometry assessment will be recorded in the source documents as pre- or post-bronchodilator.

All sites will be provided with spirometers to be used for all study assessments. Spirometry data will be transmitted to a centralized spirometry service for quality review.

Subjects (and their parents/caregivers/companions) should not be informed of their study-related spirometry results until Vertex has determined that the study has completed (i.e., CSR finalization), regardless of whether the subject has prematurely discontinued treatment.

The measured spirometric values listed below will be converted to percent predicted values using the standard equations of Global Lung Function Initiative.¹⁰

- FEV₁ (L)

■ [REDACTED]

■ [REDACTED]

■ [REDACTED]

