
Efficacy and Other Assessments Efficacy and other assessments, as indicated per protocol, may be performed by qualified personnel conducting the in-home visits. These assessments may include the following, as indicated per protocol, and per local regulation.
 
In-home Spirometry Assessment A spirometry device may be provided to subjects for in-home assessments of lung function as indicated per protocol. Sites and subjects will receive training and guidance as needed.
 
Patient Reported Outcome CFQ-R questionnaires may be provided to subjects (electronically or post mail) to be completed at home as indicated per protocol. Subjects will return these questionnaires to the site via post mail.
 
Other Assessments
 
 • ECGs • sweat chloride • [REDACTED] PK, FSH, [REDACTED] 
[REDACTED]
	
To be able to assess safety, treatment effectiveness, and quality of life measures of the CFTR modulator evaluated in the specific clinical study while ensuring subject safety.
	
All Efficacy and Other Assessments
 
[REDACTED]
 
[REDACTED]
 
VX17-659-105
 
[REDACTED]
 
[REDACTED]
 
[REDACTED]
 
Other Outcomes Only
 
[REDACTED]
 
[REDACTED]
 
[REDACTED]
 
[REDACTED]

Summary of Changes in Ongoing CF Clinical Studies for Subjects Who Cannot Travel to the Study Site

Protocol Change	Protocol Change	Protocol Change
Addendum Version 1.0, dated 24 April 2020		

Remote Monitoring Vertex has implemented remote monitoring visits where applicable, including remote source data verification, as allowed per local regulations. Remote monitoring will focus on collection of safety data, and data supporting primary and key secondary endpoints.
	
To allow for review of key data to inform on the safety of subjects receiving treatment.
 
To allow for review of other key data to inform on the objectives of the study while maintaining study integrity and the safety of subjects and site personnel.
	
[REDACTED]
 
[REDACTED]
 
[REDACTED]
 
[REDACTED]
 
VX17-659-105
 
[REDACTED]

AE: adverse event; CF: cystic fibrosis; CFQ-R: Cystic Fibrosis Questionnaire-Revised; ECG: electrocardiogram; [REDACTED]
 FSH: follicle-stimulating hormone; GCP: Good Clinical Practice; ICF: informed consent form; [REDACTED] LFT: liver function test;

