### **9.3.2.3 Sensitivity and Supportive Analysis of Secondary Endpoints**

No sensitivity or supportive analysis is planned for the secondary endpoints.

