**Table 12-1 Analysis Visit Windows for Efficacy and Safety Assessments in Study 105**

Assessment	Visit 	Target Study Day	Analysis Visit Window (in study days) 

 The analysis visit windows will be applied using the following rules for both scheduled and unscheduled visits:
 
 
1. If no numerical measurement is available within a visit window, the measurement will be considered missing for the visit.
 
2. If there is more than 1 numerical measurement available within a visit window, use the following rules:                             
 
i. The measurement closest to the target day will be used; or
 
ii. If there are multiple measurements with the same distance from the target day, the latest measurement will be used.
 
 
 
 
 For unscheduled vital signs measurements collected at Study Day 1, if any, they will be treated as post-dose observations.
 
 Weight will also be used in the threshold analysis in which the TC safety baseline will be used to calculate change.
			

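### By-visit ppFEV1 changes can include post-bronchodilator or home values that do not match the baseline test, and the SAP neither prefers matched values nor shows how many are unmatched

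*Protocol*

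**What the plan says.** **Protocol 11.6.1 (Spirometry).** The standard is "All spirometry assessments should be performed pre-bronchodilator". Two exceptions follow for subjects who forget to withhold.

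- If the parent-study Day 1 test was pre-bronchodilator, then at the later visit "a post-bronchodilator spirometry assessment will be obtained for that visit only and the visit will not be rescheduled".
- If withholding was missed on parent-study Day 1 itself, that test and the later ones are all to be post-bronchodilator: "the subject forgot to withhold his/her dose of bronchodilator, spirometry should be performed post-bronchodilator and all subsequent spirometric" measurements follow suit.

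Status is documented: "Each spirometry assessment will be recorded in the source documents as pre- or post-bronchodilator". Sites are given spirometers, and "Spirometry data will be transmitted to a centralized spirometry service for quality review".

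**COVID-19 addendum, Version 1.0 (Efficacy and Other Assessments), listing Study 105.** For subjects who cannot travel, "A spirometry device may be provided to subjects for in-home assessments of lung function as indicated per protocol". Version 3.0 adds unscheduled visits to make up assessments missed because of COVID-19.

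**SAP.** Section 9.1 takes the last non-missing value before the first parent-study dose as the efficacy baseline and lets unscheduled measurements into the visit windows. Table 12-1, footnote 2, applies when a window holds more than one value: "The measurement closest to the target day will be used", with ties going to the latest. The spirometry handling rules in 12.6 deal with age, height and race only. Section 9.3.2.2 summarises ppFEV1 and its change from parent-study baseline by visit, and 9.3.2.3 states: "No sensitivity or supportive analysis is planned for the secondary endpoints".

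**The concern.** The protocol's own principle is that a subject's follow-up tests should have the same bronchodilator status as the parent-study Day 1 test. It then accepts a known mismatch at single visits, and the addendum accepts a change of setting and possibly of device. Both are reasonable choices for running the study. The gap is in the analysis, where the SAP carries neither feature forward.

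A change score that sets a post-bronchodilator value against a pre-bronchodilator baseline contains a bronchodilator response as well as any effect of study drug. A home value set against a clinic baseline may contain a device or setting difference. The study has no concurrent control arm in which such shifts would cancel, and SAP 9.3 removes all model-based analysis, so the descriptive means are the whole ppFEV1 result. As planned, a reader could neither see how many values are unmatched nor judge what they do to the mean.

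The SAP does set validity rules for another measure. In 9.3.2.1, sweat chloride results with too little volume or outside a stated range become missing. Spirometry has no comparable rule.

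**Working it through.** The documents give no effect size, SD or precision for ppFEV1, so there is no planned figure to reproduce. The check has two parts.

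**1. Applying the SAP selection rule as written**

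Inputs (SAP Table 12-1, spirometry): OL Week 48, target day 337, window (295, 379], which spans 379 − 295 = 84 days. The protocol visit window is ±5 days (Table 3-1), so an unscheduled or make-up test can fall in the same analysis window as the scheduled one. The test days below are examples.

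| Values in the window | Distance from day 337 | Value the SAP uses |
|---|---|---|
| Clinic pre-bronchodilator day 340; home day 337 | 3; 0 | Home, day 337 |
| Clinic pre-bronchodilator day 335; home day 339 | 2; 2 (tie) | Home, day 339 (latest) |
| Clinic post-bronchodilator day 337; clinic pre-bronchodilator repeat day 344 | 0; 7 | Post-bronchodilator, day 337 |
| One post-bronchodilator or home value only | not applicable | That value, with no selection |

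For a subject with a pre-bronchodilator clinic baseline, the first three rows pass over a matched value. The fourth is likely to be the usual case, because the protocol does not reschedule the visit and home testing is meant for subjects who cannot travel. There the distance rule plays no part, and the value enters unflagged.

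A subject whose baseline was post-bronchodilator should stay post-bronchodilator under Protocol 11.6.1. That subject's changes are matched and add nothing to the problem.

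**2. Possible size**

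Shift in the by-visit mean = share of unmatched values × shift per unmatched value.

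Both inputs are assumptions, because the documents give neither: a share of 2% to 20%, and an absolute shift of 2 to 8 ppFEV1 points.

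| Share | × 2 points | × 8 points |
|---|---|---|
| 2% | 0.04 | 0.16 |
| 5% | 0.10 | 0.40 |
| 10% | 0.20 | 0.80 |
| 20% | 0.40 | 1.60 |

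SAP 9.3 displays visits down to 20 subjects per treatment group. In a group of 20, one unmatched value moves the mean by 2/20 = 0.10 to 8/20 = 0.40 points.

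The expected direction is upward for post-bronchodilator values after a pre-bronchodilator baseline. For home values it is unknown, so where both kinds occur the shifts may add or partly cancel.

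**The case against.** The strongest reply is that this is mostly silence about rare events in a secondary, descriptive endpoint. Much of that stands. The primary objective is safety, there is no primary efficacy endpoint, and the protocol already matches status for subjects whose Day 1 test was post-bronchodilator. The remaining mismatch is limited to visits where withholding was forgotten and to home tests of unknown number.

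Several stronger readings are tempting, and the documents do not support them:

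- **That home spirometry is unsupervised or escapes central review.** The addendum says qualified personnel may perform in-home efficacy assessments and provides for training. Giving a device to subjects leaves unsupervised testing possible, but the text does not state it. Nor does it say that central review is skipped.
- **That the closest-day rule is the cause.** It acts only when a window holds several values. The wider gap is that no rule looks at status or setting.
- **That home values dominate the late visits.** No count, enrolment date or data cut-off is given. The SAP introduction says the study was ended early, so whether home values reach any displayed visit is unknown.
- **That ppFEV1 is the lead endpoint.** It is listed first among the secondary endpoints, but the documents do not rank them.

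A further objection concerns the remedy. Making clinic-only values the main summary would drop subjects who could not travel, which brings its own selection, and could end the display sooner under the 20-per-group rule. That objection is sound, and it is why the all-values summary should remain the main one.

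The reply does not answer two things. When a matched and an unmatched value share a window, the stated rule can take the unmatched one. When an unmatched value stands alone, nothing in the planned output reveals it.

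**Conclusion.** The concern holds in a limited form. By-visit ppFEV1 changes can mix values that do not match the baseline in bronchodilator status or setting, and the SAP neither prefers matched values nor reports unmatched ones. That they do mix, or to what extent, cannot be said from the documents.

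The size, about 0.04 to 1.6 points in a by-visit mean, rests wholly on the assumed ranges for share and shift and on one common shift per affected value. An upward bias is the expectation for post-bronchodilator values only. The post-bronchodilator part does not depend on COVID-19; the home part does.

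No conclusion on the primary safety objective is affected. This is a low-cost improvement worth making before database lock, with medium confidence.

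**What to change.** 1. **SAP Table 12-1, footnote 2.** For spirometry, when a window holds more than one value, first prefer a clinic value with the same bronchodilator status as the value used as that subject's baseline. Then apply closeness to the target day and the existing tie rule. If no value in the window qualifies, the present rule applies unchanged.
2. **SAP 9.3.2.2 and 9.3.2.3.** Keep the all-values by-visit summary as the main one. Add a by-visit summary restricted to status-matched clinic values as supportive.
3. **Footnote to both tables.** Give the number of home values and of status-mismatched values at each visit and in each treatment group.

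The cost is a little extra programming and a smaller n in the restricted summary, which should be read with the selection of subjects able to travel in mind. One condition must be checked first: the protocol records bronchodilator status in source documents, and neither document shows that status or test setting is in the analysis dataset. If status is not available, the minimum is to report the home-value counts, if setting was captured, and to state the limitation.
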